#### **2.2.3 Safety Endpoints**

1. Adverse Events as characterized by type, frequency, severity (as graded by National Cancer Institute Common Terminology Criteria for Adverse Events [NCI CTCAE] v4.0), timing, seriousness and relationship to study treatments
2. For patients receiving SFRT to lung lesions, the development of grade 3 or greater pneumonitis that is probably or definitely attributable to either SFRT or pembrolizumab within the follow-up period will be monitored

#### **2.2.4 Biomarker Research**

1. Evaluate predictive biomarkers on pre-treatment biopsies and peripheral blood samples

Tissue based biomarkers: PD-L1 expression will be evaluated using chromogenic staining using the FDA approved DAKO PDL-1 IHC assay (22C3) and using novel quantitative immunofluorescence (QIF) based platforms. In addition to PD-L1, we will evaluate the predictive value of several other immune evasion and/or activation markers in the tumor and immune infiltrate compartments. These assays will be done in the Translational Immuno-oncology lab at the Yale University, New Haven, CT and in Collaboration with Genoptix Inc.

Peripheral Blood based biomarkers:

- a) Proteomic assays in collaboration with Biodesix and [name] lab at Johns Hopkins will be used and validated to determine predictive value
- b) Frequency and phenotypic character of PBMC subsets including DCs, MDSCs, T-cells and Natural killer (NK) cells, these will be done in collaboration with Genoptix Inc.

In addition, exploratory biomarkers using imaging-derived quantitative measurements of responses; these will be done in collaboration with the Center for Computational Imaging and Personalized Diagnostics at the Case Western Reserve University, Cleveland, OH.

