
Peripheral circulating immune cell phenotyping will be done by Genoptix Inc. In addition, MHC Dextramer® reagents will be used for detection of antigen-specific T cells pre and post CASE 1516

Protocol Amendment 7

06/06/2019

treatment. We will monitor changes of the circulating immune cell population's pre and post treatment and at the time of progression. Novel immune SEQ platforms will be used to interrogate T and B-cell receptor repertoire over time pre-post treatment and at progression. This will identify and define highly expanded clones and diversity of lymphocyte populations.

Correlations between genomic, transcriptomic and proteomic profiles of subjects tumors, and efficacy outcomes will be assessed to identify gene mutations, gene amplifications, RNA-expression levels, and protein-expression levels. Genomic sequencing of tumor cells from tissue relative to non-tumor cells from whole blood will be profiled to identify the genomic variances that may contribute to response or disease progression and provide an understanding of molecular abnormalities. RNA sequencing will be conducted to provide expression data and give relevance to DNA mutations; Quantitative proteomics analysis will be conducted to determine the exact amounts of specific proteins and to confirm expression of genes that are correlative of response and disease progression.

A recent study (NCT01176461) with a mass spectroscopy based serum proteomic assay BDX008 took pre-nivolumab treated melanoma samples from 119 patients. The same assay was independently validated with pre-treatment serum of 30 patients from a non-protocol study using PD-1 blockade regimens. The evaluation showed that patients in the non-protocol study classified as having a high likelihood of good outcome had a 74 percent lower risk of death compared to those with a profile associated with low likelihood of good outcome (hazard ratio [HR] 0.26, p=0.002). Of the 119 patients in the nivolumab trial, those with a profile predicting high likelihood of good outcome had a 50 percent lower risk of disease progression (HR 0.50, p=0.001) and a 62 percent lower risk of death (HR 0.38, p=0.001) compared to those with a profile predicting low likelihood of good outcome. (63) We will evaluate the predictive value of this assay in our trial on all the pre-treatment samples. These studies will be done in collaboration with Biodesix Inc.

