#### **2.1.2 Secondary Objective**

**Objective:**

1. To determine the progression-free and overall survival in patients with NSCLC receiving pembrolizumab, who receive Single Fraction Radiation Therapy (SFRT)
2. To determine the safety and toxicity of the combination of SFRT and pembrolizumab
3. To examine potential predictive biomarkers in tumor samples and peripheral blood in patients treated with pembrolizumab and SFRT
4. To determine the local control of SFRT in the radiated lesion(s), when SFRT is given with pembrolizumab
5. To evaluate the induction of a T-cell response in patients with metastatic NSCLC treated with radiation and the effect of radiation

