### 3 STUDY DESIGN

#### 3.1 Study Design

[figure not shown]

Figure 2 - Study Overview Flow Diagram

This is a phase II trial of pembrolizumab sequentially following focal radiation to one or more of the target lesions, in patients with stage IV Non-Small Cell Lung Cancer (NSCLC). The primary goal of this trial is to evaluate the efficacy of focal radiation (RT) to index lesion(s) as a way of enhancing the anti-tumor immune response to pembrolizumab. The primary efficacy endpoint is overall RECIST-defined response outside the radiation field. To accomplish this goal 48 patients will be enrolled in this study.

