Secondary efficacy endpoints such as progression-free survival, response duration, and overall survival will be summarized using the Kaplan-Meier method. Local control will be summarized as a frequency count and percentage. Other endpoints, such as PD-L1 expression, will be summarized as medians and ranges (e.g. proportion of cells expressing PD-L1) or frequency counts and percentages (e.g. number and percent of patient with PD-L1 expression in  $>50\%$  of cells) as appropriate.

Methods such as Fisher's exact test, chi-square tests, logistic regression (categorical data), the logrank test and proportional hazards models (time to event data) will be used to compare patient groups. These analyses are primarily exploratory and it is acknowledged that they will have relatively low statistical power.

All genomic, transcriptomic, and proteomic molecular analyses will be exploratory. These studies would be analyzed using a prospective-retrospective statistical analysis plan (SAP).

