### **8.1 Pre-Planned Subset Analysis**

Preplanned sub-set analysis will be performed based on (1) histology, (2) number of disease sites at the time of study treatment ( $\leq 4$  versus  $> 4$ ), (3) PD-L1 status (TPS  $< 50$  and TPS  $\geq 50$ ) pre-treatment, and (4) TILs status on pre-treatment samples.

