### **9.3 Clinical Supplies Disclosure**

This trial is open-label, therefore, the subject, the trial site personnel, the Sponsor and/or designee are not blinded to treatment. Drug identity (name, strength) is included in the label text. Random code/disclosure envelopes or lists are not provided.

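### The proteomic assays are to be validated for predictive value, but a single treated arm can show only that a marker is associated with outcome

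*Combined protocol and SAP*

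**What the plan says.** Section 2.2.4, item a, says the blood-based proteomic assays "will be used and validated to determine predictive value". For tissue, the same section says "we will evaluate the predictive value of several other immune evasion and/or activation markers in the tumor and immune infiltrate compartments". Of the serum assay, Section 1.2.1.3 says "We will evaluate the predictive value of this assay in our trial on all the pre-treatment samples". Secondary objective 3 (Section 2.1.2) is "To examine potential predictive biomarkers in tumor samples and peripheral blood in patients treated with pembrolizumab and SFRT", and Section 2.1.3 lists the same aim as exploratory.

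On design, Section 3.1 states "This is a phase II trial of pembrolizumab sequentially following focal radiation to one or more of the target lesions". No control group is described, and Section 9.3 adds "Random code/disclosure envelopes or lists are not provided".

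On analysis, Section 8 names Fisher's exact test, chi-square tests and logistic regression for categorical data. For time-to-event data, "the logrank test and proportional hazards models (time to event data) will be used to compare patient groups". It describes these comparisons as mainly exploratory with fairly low power. It calls all genomic, transcriptomic and proteomic analyses exploratory and assigns them to a prospective-retrospective analysis plan whose content is not given. Section 8.1 begins "Preplanned sub-set analysis will be performed based on (1) histology" and also lists number of disease sites, PD-L1 status (TPS below 50 versus 50 or more) and TILs.

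**The concern.** A marker is predictive if it changes the benefit from a treatment. It is prognostic if it goes with outcome whatever the treatment. Showing the first needs patients with and without the treatment in each marker group, and this trial has only treated patients. The plan offers no marker-by-treatment interaction, no external control for the markers, and no definition that separates the two ideas.

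The caveat about low power does not cover this. Low power warns that real effects may be missed. The problem here is that a significant result answers a different question, and more patients would not change that.

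At stake is how secondary objective 3 is reported. A significant logrank or Cox result could be presented as validating a predictive assay. A PD-L1 difference that pembrolizumab produces on its own could be credited to the combination.

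**Working it through.** **1. What one arm estimates.** For marker m and treatment T (each 0 or 1), write the log hazard as baseline + b·m + c·T + d·m·T. Here b is the prognostic effect and d the predictive effect. A claim of predictive value has the null d = 0. When T = 1 for everyone, the marker's log hazard ratio is b + d, so the logrank or Cox test has the null b + d = 0. Neither b nor d can be estimated alone. If T is split into pembrolizumab and SFRT, the same sum also contains a separate interaction for each component and one for the pair, none of them identifiable.

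**2. The plan's own figures.** The documents give no error rate or power for the marker analyses. The primary two-stage design (29 then 19 patients, stop at 6 or fewer responders, success at 12 or more) reproduces: type I error 0.195 (stated 20%), type II error 0.095 (stated 10%), early stopping 0.643 at a 20% ORR (stated 64%). The last figure matters in step 4.

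**3. Illustration for OS and PFS.** Take a marker with d = 0 and a non-zero b.
- From the documents: hazard ratios of 0.38 (death) and 0.50 (progression) for the serum assay in nivolumab-treated melanoma (Section 1.2.1.3); medians of 9.3 months (OS) and 3.0 months (PFS) in previously treated patients (Section 1.1.4); N = 48.
- Assumed: the marker is purely prognostic, two-sided 5% test, 30-70% marker-positive, exponential survival, 36 months of follow-up.

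| Prognostic HR | Logrank significant |
|---|---|
| 0.38 (OS) | about 80-88% |
| 0.50 (PFS) | 54-63% |
| 0.70 (assumed) | 17-22% |
| 1.00 | about 6% |

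Repeat simulations moved the ends of the first row by up to about three percentage points.

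Schoenfeld's formula gives a check: power = Φ(|ln HR|·√(events·p(1−p)) − 1.96), with p the marker-positive share. With 40 events and p = 0.5:
- HR 0.38: Φ(0.968 × 3.162 − 1.96) = Φ(1.10) = 0.864.
- HR 0.50: Φ(0.693 × 3.162 − 1.96) = Φ(0.23) = 0.592.

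For contrast, a separate simulation used a 9.3-month median, 24-month censoring and 50% prevalence. The single-arm Cox test was significant in 84% (HR 0.38) and 58% (HR 0.50) of runs. A marker-by-treatment interaction test in a hypothetical two-arm trial (48 per arm, treatment HR 0.7) was significant in 5.0% and 5.6%, its nominal level.

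**4. Illustration for PD-L1.** Section 1.1.4 gives a 45.2% response rate on pembrolizumab alone at a proportion score of 50% or more, in 73 of 220 validation patients (share 0.332). Suppose SFRT adds nothing. Taking the 19.4% ORR of all treated patients as the overall rate, the rate below 50% is (0.194 − 0.332 × 0.452)/0.668 = 6.6%. Rates of 10% and 15% are assumed alternatives. Power of Fisher's test at two-sided 5%, by exact enumeration:

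| Rate below 50% | 16 versus 32 patients | 10 versus 19 patients |
|---|---|---|
| 6.6% | 0.86 | 0.66 |
| 10% | 0.74 | 0.53 |
| 15% | 0.55 | 0.37 |

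The smaller split matters because, at a true 20% ORR, the trial stops at 29 patients about 64% of the time. The 15% row is generous: it implies an overall ORR of 0.332 × 0.452 + 0.668 × 0.15 = 25.0%, above the plan's 20%. Either way, a high-versus-low difference is quite likely even if radiation does nothing.

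**The case against.** The strongest reply is that the plan never says it will declare any marker predictive. It gives no threshold, alpha or decision rule for that. Objective 3 speaks only of potential markers, and Section 8 calls the comparisons, and explicitly the proteomic ones, exploratory. This stands. A reader might infer that a prognostic marker will be declared predictive, but the documents do not support that.

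A reader might also infer that every marker is to be validated. That verb is applied only to the proteomic assays; the tissue markers are to be evaluated.

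Third, the listed methods may not be the only ones, since the molecular analyses have their own plan, which is not shown. That is correct, but no method applied within one arm can supply the missing contrast.

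Fourth, the protocol sometimes uses the word predictive simply for forecasting response, and on that usage within-arm association is the relevant test. This has some force. It is a reason to state the meaning, because the word validated invites the stronger reading.

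Fifth, the percentages could be read as false-positive rates. They are not. They are power for an assumed purely prognostic marker, and nothing in Section 1.2.1.3 shows that the cited hazard ratios are purely prognostic.

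Finally, Section 8.1 only lists the PD-L1 subset and plans no test of it as evidence of a radiation effect. The 6.6% also mixes a validation-group rate, from an analysis with irRC as its primary outcome, with the ORR of all 495 patients. Both points stand, so the PD-L1 figures are illustrative only.

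**Conclusion.** The point holds as a mismatch between claim and design. Validation of predictive value is promised for the proteomic assays, and a single-arm trial cannot deliver it with any within-trial method. It is a risk of misreporting a secondary objective; the primary endpoint and the stopping rule are not affected.

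The conclusion itself needs no numerical assumption. Its practical size does: about 80-88% (HR 0.38, OS) and 54-63% (HR 0.50, PFS) rest on a purely prognostic marker, 5% alpha, 30-70% prevalence and full accrual of 48. Both fall with weaker markers or an early stop. The argument is strongest for PFS and OS. It is weaker for objective response if responses without active therapy are rare (an assumption), although a marker effect still could not be attributed to pembrolizumab, SFRT or the pair.

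It would be equally wrong to conclude that significant markers are merely prognostic, since one arm cannot establish that either.

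**What to change.** 1. In Section 2.2.4, item a, replace "will be used and validated to determine predictive value" with: will be tested for association with response, PFS and OS in treated patients. Add to Section 8, and to the matching text in Section 1.2.1.4, that prognostic and predictive effects cannot be separated in this single-arm design. State there also that within-arm results will not be reported as validating a predictive marker for pembrolizumab, SFRT or the combination. That sentence then governs the looser wording in Section 1.2.1.3 and objective 3.

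2. For the PD-L1 subset in Section 8.1, report out-of-field ORR with an exact confidence interval in each TPS stratum. For TPS 50 or more, show the cited monotherapy rate of 45.2% (95% CI 33.5-57.3) beside it, labelled descriptive because that analysis used irRC as its primary outcome. Note that the documents give no benchmark below 50%. State that a high-versus-low difference will not be interpreted as a radiation effect.

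The cost is a few sentences and one descriptive table, with no new patients, samples or assays. The price is giving up the claims of validation and predictive value, which would need a randomised or suitable external comparator with a marker-by-treatment interaction test.

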### 3 STUDY DESIGN

#### 3.1 Study Design

[figure not shown]

Figure 2 - Study Overview Flow Diagram

This is a phase II trial of pembrolizumab sequentially following focal radiation to one or more of the target lesions, in patients with stage IV Non-Small Cell Lung Cancer (NSCLC). The primary goal of this trial is to evaluate the efficacy of focal radiation (RT) to index lesion(s) as a way of enhancing the anti-tumor immune response to pembrolizumab. The primary efficacy endpoint is overall RECIST-defined response outside the radiation field. To accomplish this goal 48 patients will be enrolled in this study.

##### 3.1.1 Tumor Imaging and Assessment of Disease

The initial tumor imaging will be performed within 30 days prior to the first dose of trial treatment. CT scans are the required modality for measurable disease unless a subject has a clinical condition e.g. severe contrast allergy, or the lesions are significantly better visualized through the use of an MRI. The same imaging technique must be used for a subject throughout the study. Scans performed as part of routine clinical management are acceptable for use as the screening scan if they are of diagnostic quality and performed within 30 days prior to the first dose of trial treatment. Repeat imaging would be performed after every 2 cycles of therapy for the remainder of the on-study treatment period or more frequently if clinically indicated. CT timing should follow calendar days and should not be adjusted for delays in cycle starts or extension of pembrolizumab cycle frequencies. This protocol recommends that patients receiving pembrolizumab as standard of care after EOT will have CT scans every 9 weeks +/- 14 days until the subject experiences confirmed disease progression or starts a new antineoplastic therapy.

Subjects who discontinue trial treatment for reasons other than disease progression should also receive tumor imaging every 9 weeks +/- 14 days until the subject experiences confirmed disease progression or starts a new antineoplastic therapy.

Disease progression for trial eligibility will be according to RECIST 1.1 criteria. Local reading (investigator assessment with site radiology reading) will be used to determine eligibility and for subject management. De-identified imaging will also be obtained from all participating sites for

imaging correlative studies to be done by collaborators at Case Western Reserve University Biomedical Engineering group.

### **3.1.2 Tumor Tissue Collection and Correlative Studies Blood Sampling**

#### **3.1.2.1 Correlatives in Biopsy Tissue**

All the tissue based immunological correlatives PD-L1 expression and other exploratory correlatives will be performed by NavigateBiopharma and in the Translational Immunooncology Laboratory lab at the Yale University. Both these laboratories are specialized in measurement of immune biomarkers and have access to CLIA-compliant facilities.

- i. *Measurement of Tumor infiltrating immune cells on pre-treatment and post treatment biopsies*: The automated quantitative spectral multiplexing platform for evaluation of immune biomarkers is highly novel. We have previously developed and validated ways to reproducibly measure and quantify TILs and immune biomarkers by QIF. (51, 59, 61) To understand the tumor immune landscape, we will characterize the immune infiltrates in the samples using a previously described and validated assay to objectively interrogate different lymphocyte subsets. (59) This assay comprises the simultaneous staining and measurement of tumor cells (cytokeratin), T cells (CD3), cytotoxic T cells (CD8) and B lymphocytes (CD20). The signal intensity and amount of cells will be measured using informatic tools as described for PD-L1. These will be done in collaboration with Tumor immunology lab at Yale to develop and validate several immune biomarker panels for potential use in the clinical setting. This collaboration will expand on our previous work.
- ii. *Measurement of several immune biomarkers in the tumor and stromal compartments on pre-treatment and post treatment biopsies*: PD-L1 expression will be determined for all patients on pre-treatment samples per standard of care using the DAKO PD-L1 assay in the Yale CLIA lab. Positivity will be determined by the presence of any (non-nuclear) PD-L1 signal present in intact tumor and/or stromal cells within the tumor region of the tissue examined, as evaluated by a pathologist in preparations stained with chromogenic immunohistochemistry for PD-L1 and counterstained with hematoxylin. Operationally, a positivity threshold of signal present in >1% of cells will be used. An additional 3-tiered semi-quantitative categorical result will be rendered by the pathologist based in the estimation of the percentage of positive cells including 1+ (<30%), 2+ (30-<60%) and 3+ (60-100%). PD-L1 negative cases will be those with absence of any detectable signal in the sample tested and with appropriate tissue and staining controls.

In addition to chromogenic PD-L1 IHC using a novel platform, we can increase specific staining of multiple tissue biomarkers (PD-L2, B7H4, TIM-3, VISTA, LAG-3, IDO-1 etc.), and are able to reach 6-plex and beyond in a single image retaining the morphologic context of the tumor. The incorporation of such novel approaches could positively impact the value of tissue biomarker determination for anti-cancer immunotherapies. Finally, additional correlative studies using novel approaches with higher sensitivity and throughput, such as the Luminex assay and CyTOF massspect based cytometry, will be pursued once these platforms are appropriately standardized.

- iii. *Omics Testing*: We will evaluate the genomic, transcriptomic, and proteomic profile of subjects' tumors to identify gene mutations, gene amplifications, RNA-expression, and protein-expression using the Nantomics "Omics platform". The exploratory genomics, transcriptomic, and proteomics molecular profiling will be performed on formalin-fixed, paraffin embedded (FFPE) tumor tissue and whole blood samples (subject matched normal comparator against the tumor tissue) by next-generation sequencing and mass spectrometry-based quantitative proteomics. Collection of tumor tissue and whole blood is mandatory for this study, unless an exception is approved by the sponsor investigator. See lab manual for tissue collection requirements.
- iv. *Next Generation Sequencing for T-cell receptor clonality*: TCR sequencing and clonality quantification on pre-and post-treatment samples will be performed using ImmunoSeq assay in a multiplexed PCR method using forward primers specific to TCR V $\beta$  gene segments and reverse primers specific to TCR J $\beta$  gene segments. In addition, using Immune Repertoire CaptureTM (IRCTTM) technology we will evaluate immune response, enabling the identification and generation of functional human antibodies and TCRs. This delivers an unparalleled quantitation of the adaptive immune response. This will be done in collaboration with Atreca Inc.
- v. *Pharmacodynamic analyses*: The intended molecular pharmacodynamic effect of oral THU-decitabine is depletion of DNMT1 in tumor tissue. This will be measured by QIF. DNMT1-depletion is expected to induce p53-independent cell cycle exits, with downregulation of MYC and upregulation of p27/CDKN1B. This will be measured by QIF also. Finally, the intracellular accumulation of decitabine to deplete DNMT1 depends on relative expression in the cancer cells of pyrimidine metabolism enzymes DCK, CDA and UCK2, and also the growth fraction of the malignancy, measured by surrogates such as KI67. These parameters will also be measured by QIF.

